#### **RCT A ARM 2: SOTALOL**

**Initiate treatment with oral Sotalol 80 mg TID or 120 mg BID (240 mg/day).**

**SVT WITHOUT HYDROPS (RCT B): DIGOXIN vs. FLECAINIDE****RCT B ARM 1: DIGOXIN**

Aim: therapeutic maternal trough level of *1.0-2.0 ng/ml* or 1.3-2.6 nmol/L (please verify the units your laboratory reports).

→ *Oral or intravenous loading dose: Initiate treatment with 0.5 mg Digoxin q 12 h* (total 4 doses over 48 hours) followed by:

→ *Oral maintenance dose:* it is recommended to obtain maternal digoxin trough level 12 hours after the 4th loading dose just prior to the administration of the 1st maintenance dose\* → await the result and adjust the 1st maintenance dose according to the trough digoxin level as followed:  
(\*alternatively, a digoxin level may be obtained prior to the 4th dose to adjust the 1st maintenance dose if levels are not rapidly measured in your center)

Trough level (nmol/L)	Trough level (ng/ml)	Maintenance digoxin dose	Route
2.6 to <2.9	2 to <2.3	0.25 mg/day	Oral
1.9 to <2.6	1.5 to <2	0.375 mg/day	Oral
1.5 to <1.9	1.2 to <1.5	0.5 mg/day	Oral
1.0 to <1.5	0.8 to <1.2	0.75 mg/day	Oral
<1.0	<0.8	1 mg/day	Oral
≥2.9	≥2.3	0 mg/day until digoxin level is <2 ng/ml	

→ recommended to repeat maternal trough level until steady state therapeutic drug levels are obtained.

*If using IV Digoxin loading see additional recommendations for IV Digoxin administration below.*

**RCT B ARM 2: FLECAINIDE**

Aim (if available): therapeutic maternal drug level of *0.2-1 µg/ml*

**Initiate treatment with oral Flecainide 100 mg TID (300 mg/day).**

**SVT WITH HYDROPS (RCT C): DIGOXIN PLUS FLECAINIDE vs. DIGOXIN PLUS SOTALOL****RCT C: ARM 1 DIGOXIN Plus FLECAINIDE****DIGOXIN**

Aim: therapeutic maternal trough level of *1.5-2.0 ng/ml* or 1.9 – 2.6 nmol/L (please verify units that your laboratory reports).

→ Intravenous or oral loading dose: **Initiate treatment with 0.5 mg Digoxin q 8 h** (total 4 doses over 32 hours)

→ *Maintenance dose*: It is recommended to obtain maternal digoxin trough level preferably 10-12 hours after the 4th loading dose, prior to administrating the 1st maintenance dose. Adjust the 1st maintenance dose according to the trough digoxin level as followed:

Trough level (nmol/L)	Trough level (ng/ml)	Maintenance digoxin dose	Route
2.6 to <2.9	2 to <2.3	0.25 mg/day	Oral
1.9 to <2.6	1.5 to <2	0.375 mg/day	Oral
1.5 to <1.9	1.2 to <1.5	0.5 mg/day	Intravenous or Oral
1.0 to <1.5	0.8 to <1.2	0.75 mg/day	Intravenous or Oral
<1.0	<0.8	1 mg/day	Intravenous or Oral
≥2.9	≥2.3	0 mg/day until digoxin level is <2 ng/ml	

→ recommended to repeat maternal trough level until steady state therapeutic drug levels are obtained in the upper therapeutic range.

*If using IV Digoxin see additional recommendations for IV Digoxin administration below.*

#### **PLUS FLECAINIDE:**

Initiate above Digoxin treatment in combination with **oral Flecainide 100 mg TID** (300 mg/day).

#### **RCT C ARM 2: DIGOXIN PLUS SOTALOL:**

##### **DIGOXIN**

Aim: therapeutic maternal trough level of 1.5-2.0 ng/ml or 1.9 – 2.6 nmol/L (please verify units that your laboratory reports).

→ Intravenous or oral loading dose: **Initiate treatment with 0.5 mg Digoxin q 8 h** (total 4 doses over 32 hours)

→ *Maintenance dose*: It is recommended to obtain maternal digoxin trough level preferably 10-12 hours after the 4th loading dose, prior to administrating the 1st maintenance dose. Adjust the 1st maintenance dose according to the trough digoxin level as followed:

Trough level (nmol/L)	Trough level (ng/ml)	Maintenance digoxin dose	Route
2.6 to <2.9	2 to <2.3	0.25 mg/day	Oral
1.9 to <2.6	1.5 to <2	0.375 mg/day	Oral
1.5 to <1.9	1.2 to <1.5	0.5 mg/day	Intravenous or Oral
1.0 to <1.5	0.8 to <1.2	0.75 mg/day	Intravenous or Oral
<1.0	<0.8	1 mg/day	Intravenous or Oral
≥2.9	≥2.3	0 mg/day until digoxin level is <2 ng/ml	

→ recommended to repeat maternal trough level until steady state therapeutic drug levels are obtained in the upper therapeutic range.

*If using IV Digoxin see additional recommendations for IV Digoxin administration below.*

## PLUS SOTALOL

Initiate above Digoxin treatment in combination with **oral Sotalol 160 mg BID** (320 mg/day).

### IV DIGOXIN: additional recommendations

For RCT A, B or C Digoxin can be administered as oral tablets or IV. For IV the Digoxin Injection can be administered undiluted or diluted with a 4-fold or greater volume of 0.9% NaCl injection, or 5% Dextrose Injection. The use of less than a 4-fold volume of diluent could lead to precipitation of the digoxin. Immediate use of the diluted product is recommended. Slow infusion of digoxin over a period of 5 minutes or longer is preferable to bolus administration. Rapid infusion of digitalis glycosides has been shown to cause systemic and coronary arteriolar constriction, which may be clinically undesirable. Mixing of intravenous digoxin with other drugs in the same container or simultaneous administration in the same intravenous line is not recommended.

### 7.6.1 CONCOMITANT MEDICATIONS

Medication to be avoided during trial participation or, if no alternative exists, used with caution and appropriate monitoring of the QTc, include medications that prolong QT and/or increase risk for Torsades de Pointes (TDP) (List available online at: <https://crediblemeds.org/healthcare-providers/>). Concomitant medication use of pentamidine is to be avoided and additional anti-arrhythmics to be used with caution. See relevant drug monographs for detailed information on precautions and possible drug interactions.

## 7.7 STUDY CONDUCT

**PATIENT CARE.** The treating physician will be responsible for the medical care of enrolled participants and medical oversight will be the responsibility of the local PI. The type and frequency of standard clinical care patient assessments, should not differ from a non-study participant with the same clinical findings. The medical management of study participants should also not differ from a non-study patient with comparable clinical findings. This includes, in agreement with accepted management guidelines, the *recommendation* to commence 1st line treatment as well as any significant changes in drug therapy in-hospital to allow close monitoring of the fetal-maternal treatment effects and well-being by ECG, echocardiograms, digoxin level, and biophysical profile, until fetal cardioversion or heart rate control is achieved. After discharge from hospital, serial fetal heart rate monitoring to birth by the physician (usually by weekly fetal echocardiograms) and the mother (by daily Doppler monitoring at home) is *recommended* to detect SVA recurrences and to allow treatment adjustments, as required.

What will differ from standard procedures is the requirement to assess and document AEs, including whether the event is serious, the severity, causality and expectedness of the event, as well as to follow-up on and document the outcome. The sponsor PI ([name] and his team) will assume the role of Medical Monitor/Advisor and should be contacted for questions regarding the study and patient safety (e-mail: [contact]).

**TREATMENT.** All management decisions after initiation of the first-line treatment will be at the discretion of the primary physician. This means that the responsible physician is at any time free to adjust the dosage of 1st line medication, to add or switch to a 2nd line agent, or to deliver a fetus based on his/her own clinical judgment. It is

however important to recognize that 1st line treatment effects are incremental and it will take several days to reach therapeutic fetal drug levels with transplacental medication. A *premature change to 2nd line therapy prior to 3-7 days of therapy is therefore not advised* unless there is significant worsening of the fetal state (e.g. new hydrops), the SVA pattern (>20% increase in SVA rates and duration), or both. Members of the FAST Trial steering committee have developed consensus-based recommendations [Care Maps] to adjust the prenatal pharmacotherapy to the most common treatment outcomes and clinical scenarios, e.g. if 1st, 2nd or 3rd line treatment appears ineffective. Care Map recommendations may include: a) no change in therapy (sinus rhythm; ↓ SVA <10% of time); b) escalation of drug dose (some SVA response); or c) addition of or change to different medication (no SVA response). The responsible physician is free to follow the recommendations or to elect treatment that differs from the Care Map. Cross over to a different medication, fetal demise, preterm delivery, and SVA that persists to birth will be considered as *1st line treatment failure*. Removal of an agent from treatment following sustained conversion to a normal rhythm (*treatment success*) does not constitute treatment failure.

Following sustained conversion to a normal rhythm of at least 24 hours (*acute 1st line treatment success*), it is recommended to not change the successful treatment until birth if the treatment is tolerated and the SVA does not recur. Any new documentation of fetal SVA on maintenance therapy that is *confirmed by fetal echocardiography or by heart rate monitoring during labor* will be considered as *maintenance treatment failure*. Near-complete suppression of SVA does usually not require a change in maintenance therapy. Maternal drug therapy will be maintained until time of delivery and discontinued immediately thereafter. The *choice of postnatal neonatal drug therapy* will be at the discretion of the primary physician. Postnatal outcomes will be assessed to a minimum of 1 month of age.

**7.8 PROCEDURES OUTSIDE OF STANDARD CARE.** The conduct of the RCT sub-studies requires procedures that are not part of usual patient management and documentation of findings. This includes:

- The process of randomization to 1st line therapy
- The mode of supply and dispensation of 1st line medication
- Home fetal heart rate monitoring (FHRM) offered to participants
- The documentation of de-identified study results in CRFs and REDCap
- Participant questionnaires (AEs and fetal heart rate monitor), medication diary, fetal heart rate monitoring log
- AE assessment and reporting
- Adherence rate to treatment assessment

**DATA DOCUMENTATION:** The table of events summarizes the study conduct and procedures

**PRENATAL.** Following randomization and treatment initiation, sites must upload *de-identified images* to REDCap of pre-treatment M-mode and/or Doppler still images, 2-dimensional images of the fetal abdomen, and 12-lead maternal ECG for review and confirmation of diagnosis by the FAST Trial Echo Core Lab. Moving clips confirming the fetal SVA mechanism should be sent via secure file transfer for Echo Core Lab review.

Following treatment initiation, it will be possible to document the result of up to 25 prenatal participant encounters in REDCap (from day 1 of treatment to birth or death). Pre-natal participant encounters during

maintenance therapy will occur every 1-3 weeks as clinically indicated/opinion of the Investigator. Information that is captured includes:

- Date of encounter → gestational age at encounter and total days of prenatal treatment
- Patient care: inpatient versus outpatient; methods of maternal-fetal surveillance
- Participant adherence to therapy (first-line therapy only)
- Maternal findings\*: Diagnoses; adverse symptoms (questionnaire); ECG; digoxin level
- Fetal findings\*: diagnoses; rhythm; atrial and ventricular rate; SVA characteristics; date of cardioversion; fetal state; cardiac function, AV regurgitation; umbilical venous flow, FHRM data (log)
- Current medication and treatment recommendations to next encounter
- Rationale of treatment modifications and adherence to Care Maps
- File uploads of new clinically relevant test results#: if relevant new findings, upload maternal 12-lead ECG, M-mode and/or Doppler of current rhythm.

\* = All data will be entered into CRFs and into REDCap. # = images of new, relevant results to be uploaded into REDCap (de-identified) or sent via secure file transfer.

#### PERINATAL.

- Pregnancy and treatment outcomes including date and gestational age at birth or demise
- Number and duration of treatment related maternal hospitalization to birth and adverse outcomes
- Mode of delivery

POSTNATAL. Outcome of live-born babies and their mothers to at least 30 days of corrected postnatal life.

- Newborn:
  - Date and gestational age at birth
  - Weight, height, and head circumference at birth
  - Gender
  - APGAR scores
  - Neonatal complications
  - Neonatal SVA (none, induced or spontaneous) and if applicable SVA mechanism and treatment
  - Neonatal outcome to 30 days
  - Date of discharge from hospital → length of in-hospital care (birth to discharge)
  - Upload: neonatal ECG; SVA tracing if applicable
- Maternal:
  - Delivery complications, management and outcome
  - Date of discharge from hospital → length of in-hospital care (delivery to discharge)
  - Upload: FHRM Questionnaire if completed

**MEDICATION-RELATED PROCEDURES:**

**DRUG SUPPLY.** In accordance with institutional and national regulations, 1st line medication to birth or treatment failure will be supplied as specified in site agreements and dispersed as agreed with the pharmacy and in adherence with national regulatory guidelines. There may be brief periods of time when 1st line medication will be dispensed from an alternative clinical supply such as during labour and delivery. If this occurs it will be documented but not recorded as a protocol deviation, however attempts should be made to obtain information regarding the lot number and manufacturer. All responsibility for study medication, packaging and labeling is delegated to the Site Investigator as outlined in the Study Agreement. As this is a study of 1st line treatment only, once the participant changes therapy to second line medication the medication will be supplied from clinical supply and documentation of accountability will no longer be applicable.

**ACCOUNTABILITY.** An accurate and current accounting of the dispensing and return of study drug for each subject will be maintained on an ongoing basis by an *Investigational Product Accountability Log* kept by the Site Investigator. The amount of study drug dispensed and returned by the subject will be recorded in this log. The responsibility of keeping records of drug accountability will be delegated to the study site. This Accountability Log is only required for 1st line study medication for the RCTs.

**COMPLIANCE AND ADHERENCE.** Most mothers with fetal SVA understand the importance of regular drug intake to improve the chances of a normal pregnancy outcome and non-compliance is highly unusual. Nonetheless, participant compliance should be assessed at each visit (for 1st line study medication) by inspecting the medication remaining since last dispensing. Adherence rate to treatment since last visit will be calculated as percentage of the prescribed medication that has been taken by the participant since last encounter. In the event that the mother is admitted to hospital and is administered treatment drugs from the hospital pharmacy and not from her personal study medication, self-reporting of dosage will be taken into account when determining adherence. Non-compliance may be suspected if the adherence rate is <80%, is self-reported, digoxin level tests turn out too low or is negative, among others.

**7.9 RCT CENTERS & DURATION.** Requirements of a study site to be considered eligible to participate in the FAST Therapy RCT include:

- The centre provides the primary care of RCT participants from the time of SVA diagnosis to birth or death.
- Neonatal and maternal outcomes to 30 days after birth is ascertained.
- The site investigator/site have the experience, the commitment, and the infrastructure to successfully conduct this research.
- REB approval has been obtained including, if applicable, for affiliated institutions.
- Regulatory approval has been obtained by the study site or, if applicable, the national coordinating center.
- Contracts (data share, legal and financial agreements) have been finalized.

With an anticipated 50 average sized centers and 80% consent rates per RCT, actual study periods are expected to take 1.9 years (SVT without hydrops), 3.8 years (AF without hydrops), and 4.4 years (SVT with hydrops), respectively. This will allow follow-up to 30 days after birth of corrected age of all study participants. Study

completion <5 years will require a minimum of 20 average sized centers in RCT B (SVT without hydrops RCT: 4.7 years), 40 centers in the RCT A (AF without hydrops: 4.7 years), and 45 centers in RCT C (SVT with hydrops: 4.9 years).

**FOLLOW UP STUDIES.** Participant outcomes will be ascertained to 30 days after birth or death. To be able to provide participants with information regarding the outcome of the study and to request their participation in follow-up studies (for example to determine the neurodevelopmental outcome of survivors beyond 1 month of life) we will request the parental permission for electronic contact information (e-mail). The information will be sent to the sponsor via secure file transfer and stored securely at SickKids with only study ID number and e-mail on the form.

**7.10 OUTCOME MEASURES.** Identical outcome measures will be used for RCT and Registry subjects. We expect significant differences in various outcomes among drug regimens based on our preliminary work.

#### **PRIMARY OUTCOME**

- Term delivery ( $\geq 37$  0/7 weeks gestation) with a normal cardiac rhythm (ECG).

#### **SECONDARY OUTCOME**

- Proportion of participants with cardioversion over time
- Proportion of participants with treatment failure
  - Number of participants with treatment failure compared to number of participants with successful treatment.
  - Treatment failure is defined as one of the following:
    1. cross-over to another drug
    2. SVT/AF that persists to birth
    3. preterm birth
    4. death
- Cause of death (prenatal, postnatal)
- Proportion of participants with arrhythmia related death
- Average gestational age at birth
- Birth weight (z-scores)
- Average days of maternal and neonatal hospitalization related to SVA therapy
- Maternal prevalence of pregnancy/treatment-related AEs and outcomes
- Proportion of AEs / adverse outcomes (prenatal, postnatal)

The primary outcome measure is absolute (term delivery without tachyarrhythmia) with no room for interpretation. Secondary outcomes will be the time interval from treatment initiation to the beginning of permanent cardioversion, and once established, the freedom from SVA recurrence on maintenance therapy. Only the final outcome will be considered to classify cases. Cross-over to another agent, fetal demise, development of fetal hydrops, and delivery for SVA will be considered treatment failures. Any recurrence of fetal SVA after

documentation of a normal cardiac rhythm >24 hours by echocardiography will be classified as maintenance treatment failure.

**7.11 STATISTICAL ANALYSES.** All statistical analyses using SAS (SAS Institute, Cary NC) with standard settings will be performed by very experienced statistician from the Cardiovascular Data Management Centre (CVDMC) at SickKids. As a general precept, all 3 RCTs will be analyzed separately. RCT analyses will be performed on an *intention-to-treat basis*, although a separate subgroup analysis will be performed. Descriptive statistics for all study variables, for each study groups separately, will be created using means with standard deviation, median with inter-quartile range, and frequencies as appropriate. Baseline characteristics that should be equally distributed between groups through randomization (age at diagnosis, baseline fetal heart rate, incessant vs. intermittent SVA, maternal age) will be assessed in a test of randomization. The test of randomization will be performed using Fisher’s exact test for categorical variables and Student’s t-test (with Satterthwaite method for variance estimation) for continuous variables.

The **PRIMARY OUTCOME** (proportion of term deliveries without SVA) will be a binary outcome (yes/no). For this type of outcome, the proportion of participants in each therapy arm will be compared using logistic regression models (PROC LOGISTIC) with likelihood ratio test to determine regression model fit, Wald chi-square test from maximum likelihood estimates (Fisher’s scoring technique) to determine statistical significance of the therapy arm and c-statistic from the regression model’s area under the curve (AUC) to measure model accuracy. Effect size estimate and standard error will be converted into odds ratio with 95% confidence (95% CI) limits to facilitate comparisons between the different trials.

**SECONDARY OUTCOME** will also be expressed as binary variables (incl. proportions of participants: requiring 2nd line therapy and 3rd line therapy; with SVA recurrence on maintenance therapy; delivery without SVA termination; death <1 month; etc.) will be assessed between the different therapy arms in the same way as the primary outcome. For outcomes with time dependent variables (proportion of participants with cardioversion over time; timing of mortality from initiation of therapy), Kaplan-Meier survival curves will be used to depict the event proportion over time for each group. Single phase parametric hazard regression model (PROC PHREG) will be used to compare the 2 therapy arms (with likelihood ratio test to determine regression model fit and maximum likelihood estimates chi-square to determine statistical significance of the therapy arm. Effect size estimate and standard error will be converted into hazard ratio with 95% CI to facilitate comparisons between the different trials. Finally, for outcomes with continuous variables (average gestational age at birth/birth weight z-score; average days of neonatal hospitalization related to SVA therapy), linear regression models using maximum likelihood estimates for parameter estimation will be used (PROC GENMOD: Akaike's information criterion (AIC) criterion to assess regression model fit; Wald chi-square test from maximum likelihood estimates). Effect size estimate and standard error will determine the difference between the therapy arms in the same original units of measurement as the outcome.

**SUB-ANALYSIS** will attempt to determine the factors associated with successful RCT outcomes. To accomplish this, we will use our primary outcome as the dependent variable. Fetal factors (age at diagnosis), SVA characteristics (heart rate; arrhythmia pattern; SVT subtypes) and treatment metrics (agent(s); dose) will be considered as potential independent variables. In a first, all variables will be evaluated separately in univariable

logistic regression models. Those with p-values <0.20 in those models will then be selected for further evaluation in a bootstrap bagging algorithm (500 random resamples). Those variables with high reliability (selected in >50% of the random resamples) will be included in a multivariable logistic regression model (PROC LOGISTIC) with likelihood ratio test to determine regression model fit, Wald chi-square test from maximum likelihood estimates (Fisher's scoring technique) to determine statistical significance of the therapy arm and c-statistic from the regression model's area under the curve (AUC) to measure model accuracy with backward selection of variable (p<0.05 to enter) to obtain a final model. Effect size estimate and standard error will be converted into odds ratio with 95% CI to facilitate comparisons of effect size between the different covariates. This final model would indicate factors associated with greater odds of positive outcome and, providing that analog results are found between the effects of 1st line therapy between the 2 models (primary RCT analysis as above and sub-analysis).

**FREQUENCY OF ANALYSIS.** Pre-specified interim analyses of the 3 strata will be performed separately at 50% of enrolment. Each analysis will focus on the primary outcome and safety report including review of between-groups differences and individual review of AEs, other maternal, fetal and infant outcomes, and other safety concerns, if any. All interim analyses will be blinded (with potential un-blinding at the request of the DSMB) as to not influence the final analysis.

**SUBGROUP ANALYSIS.** Additional subgroup analyses will include comparisons with registry participants and impact of tachycardia rates: 1) cardioversion rates over time of RCT participants with SVT and AF  $\pm$  hydrops; and 2) tachycardia rates of cases with persistent SVA at  $\pm$ 1 week of acute therapy (all arms).

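### The treatment-failure outcome counts an undefined cross-over and does not list addition of a drug, so a fetus converted only after an add-on can be scored as a first-line success

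*Combined protocol and SAP*

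**What the plan says.** Failure of first-line treatment is defined in three places.

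- Section 7.7 (Treatment): "Cross over to a different medication, fetal demise, preterm delivery, and SVA that persists to birth will be considered as" first-line treatment failure.
- Section 7.10, numbered list under the secondary outcomes: item 1 is "cross-over to another drug". The other items are persistence of the arrhythmia to birth, preterm birth and death.
- Section 7.10, narrative below the list: "Cross-over to another agent, fetal demise, development of fetal hydrops, and delivery for SVA will be considered treatment failures". The same paragraph says that cases are classified by their final outcome alone.

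Section 7.7 also describes what the physician may do once first-line treatment has begun. The options include "to add or switch to a 2 nd line agent", and the Care Maps offer "addition of or change to different medication (no SVA response" as a separate option from raising the dose. One further rule concerns multi-drug treatment: "Removal of an agent from treatment following sustained conversion to a normal rhythm" is not failure. There is no matching rule for an agent that is added.

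Section 7.11 lists the proportions needing second-line and third-line therapy as separate binary secondary outcomes, compared between arms in the same way as the primary outcome.

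**The concern.** The failure outcome is meant to show whether the assigned first-line regimen was enough. Cross-over normally means leaving one treatment for another. The protocol itself uses different words for adding and for switching, so an add-on does not clearly fall under cross-over. A mother kept on the randomized drug with a second agent added, whose fetus then converts and is born alive at term in normal rhythm, meets no criterion on any of the three lists. Classification by final outcome alone favours scoring her as a success. The effect of the combination is then credited to the first-line drug. In RCT A or B the added agent may even be the comparator.

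The trial is open label, and treatment after initiation is at the physician's discretion. If physicians tend to add in one arm and switch in the other, equally effective first-line drugs can show different failure proportions, or a real difference can be masked. In RCT C, which starts with two drugs, the same gap applies to a third.

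**Working it through.** **Step 1: set the definitions beside the permitted actions.**

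| Place | Change of drug | Addition of a drug | Other criteria |
|---|---|---|---|
| 7.7, Treatment | failure | not listed | fetal demise, preterm delivery, SVA persisting to birth |
| 7.10, list | failure | not listed | arrhythmia persisting to birth, preterm birth, death |
| 7.10, narrative | failure | not listed | fetal demise, new hydrops, delivery for SVA |
| 7.7, physician's options | permitted | permitted, named separately | n/a |
| 7.7, Care Map for no response | option | option, named separately | n/a |

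An add-on case with conversion, no new hydrops and live birth at term in normal rhythm escapes all three lists. Add-on cases that end in preterm birth, death or persistent SVA are failures under the 7.10 list in any event. The cases at issue are therefore a subset of the term, normal-rhythm births.

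**Step 2: planning figures (Section 3.2).** The normal primary outcome is 30% versus 50% in RCT A and in RCT C, and 55% versus 75% in RCT B, with two-sided alpha 0.05 and power 80%. The pooled-variance formula is

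n per arm = [1.960 × √(2p̄(1−p̄)) + 0.8416 × √(p₁(1−p₁) + p₂(1−p₂))]² / (p₂−p₁)².

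- RCT A and C: [1.960 × √0.48 + 0.8416 × √0.46]² / 0.04 = 93.0, so 93.
- RCT B: [1.960 × √0.455 + 0.8416 × √0.435]² / 0.04 = 88.1, so 89.

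These match the stated 93, 89 and 93 per arm (186 + 178 + 186 = 550). The primary outcome does not depend on how an add-on is classified, so none of these figures changes.

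**Step 3: number whose class depends on the reading.** Let q be the share of term, normal-rhythm births that followed an add-on. The documents do not give q; 10-50% is an assumed range. The number per arm is n × p × q.

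| q (both arms) | RCT A or C, inferior vs superior | RCT B, inferior vs superior |
|---|---|---|
| 10% | 93×0.30×0.10 = 2.8 vs 93×0.50×0.10 = 4.7 | 89×0.55×0.10 = 4.9 vs 89×0.75×0.10 = 6.7 |
| 20% | 5.6 vs 9.3 | 9.8 vs 13.4 |
| 50% | 14.0 vs 23.3 | 24.5 vs 33.4 |

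**Step 4: effect on the failure comparison.** For illustration, treat failure under the literal wording as absence of a normal primary outcome and ignore cross-overs. If an add-on also counts, failure = 1 − p(1−q).

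| q inferior / superior | RCT A or C failure | Difference (points) | RCT B failure | Difference (points) |
|---|---|---|---|---|
| Literal reading | 70% vs 50% | 20 | 45% vs 25% | 20 |
| 20% / 20% | 76% vs 60% | 16 | 56% vs 40% | 16 |
| 20% / 40% | 76% vs 70% | 6 | 56% vs 55% | 1 |
| 50% / 20% | 85% vs 60% | 25 | 72.5% vs 40% | 32.5 |

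Depending on how add-on use falls between the arms, the literal reading can overstate the difference (20 against 6 or 1) or understate it (20 against 25 or 32.5).

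**The case against.** The strongest reply is that the protocol can be read as covering add-ons already. Section 7.7 calls an added drug second-line and cautions against an early change to second-line therapy without a separate caution about adding. The drug-supply paragraph in Section 7.8 provides first-line drug until birth or treatment failure and ends accountability once therapy changes to second line. An adjudicator could conclude that any move to second line, by either route, is cross-over. This stands in part. The text permits the misclassification but does not compel it, so a reader who infers that the plan requires add-on cases to be scored as successes goes too far. The reply does not remove the problem, because an undefined term would have to be settled by judgement in an open-label trial.

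Second, Section 7.11 already compares the need for second- and third-line therapy. That is a real safeguard: add-on use will be visible. It leaves the failure classification as it is, and the two secondary results could disagree.

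Third, a reader might size the problem from Fig. 1 in Section 2.5, where 100 − 63 = 37% of SVT and 100 − 41 = 59% of AF cases were unconverted at day 10. The documents do not support that base. Many of those cases would fail anyway through preterm birth, persistence or death. If, say, 75% of the AF cases received an add-on, 0.59 × 0.75 × 93 = 41 per arm would be affected, more than the 0.30 × 93 = 28 normal outcomes expected in the inferior arm of RCT A. The 75 SVT cases also include hydropic fetuses, whom RCT B excludes, and the cohort includes the agents dropped for each rhythm.

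Finally, nothing in the documents shows that add-on habits will differ by arm, or in which direction. The bias is a possibility, not a forecast.

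**Conclusion.** The definition should be corrected. It concerns one secondary outcome: cross-over is undefined, addition of a drug is missing from all three failure definitions, and the literal reading credits combination rescue to the assigned first-line regimen. At an assumed 20% add-on share among term, normal-rhythm births, about 6 versus 9 participants per arm in RCT A or C and about 10 versus 13 in RCT B would change class. Over 10-50% the range is about 3 versus 5 to 14 versus 23, and about 5 versus 7 to 24 versus 33. These counts rest on the planning rates and on an add-on share that the documents do not give. They also assume that the add-on cases are not already failures through cross-over. A reader might infer that the trial's main conclusion is at risk. It is not, because the primary outcome of term delivery in normal rhythm does not use this classification.

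**What to change.** In Section 7.7 and in both places in Section 7.10, use one definition for outcome classification: **cross-over to, or addition of, any antiarrhythmic drug not in the assigned first-line regimen**. Keep the rule that removing an agent after sustained conversion is not failure. Add no new time limit. A limit such as *before sustained conversion* would reclassify switches made after conversion, which now count as failure. Settle the wording before anyone sees failure results by arm.

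Costs and side effects:

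- Because the current cross-over criterion is kept and one is added, failure proportions can only stay the same or rise in each arm.
- A drug added after conversion, for example for recurrence, would also count, as a switch at that stage does now.
- Current medication and cardioversion date are already captured at encounters (Section 7.8), so no new form is needed. Exact add-on start dates may have to be inferred, since maintenance encounters are 1-3 weeks apart.
- The drug-supply paragraph in Section 7.8 also refers to treatment failure, so the text should say that the definition serves outcome classification only and leaves supply and patient care unchanged.

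When the three definitions are aligned, their remaining differences also need reconciling: the 7.10 narrative has new hydrops and delivery for SVA where the other two have preterm birth or delivery.
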